#### 3.4.5 Power Analysis

The qualitative sub-study sample during the pilot phase will be limited to one focus group with patients and three in-depth interviews with providers.

In the main phase, we will conduct two focus groups with 6-8 patients, one in-depth interview with participant who have dropped out of treatment, or not completed SVR12 testing, or didn't start treatment, two in-depth interviews with 2-4 providers.

In order to conduct the proposed analysis, a sample size of 900 patients, provides more than sufficient power to conduct the proposed analyses. The use of principal component analysis (PCA), for parsimoniously grouping variables is a reductionist strategy to explain groupings of variables with multiple collinearity. The time-dependent analysis allows for detection of even small changes in the primary and secondary outcome, even if the primary (or secondary) outcome increases any of the study groups. Thus, as few as 200-300 participants in each group is more than sufficient to achieve sufficient power (>0.95) to detect an intervention effect, including a synergistic effect of intervention^[No ECHO] x intervention^[ECHO] and even by site type (by varying degrees of integration), over time.

### 3.5 Research methods for Aim 3

Aim 3: To evaluate the effectiveness of SHIM in improving the HCV treatment cascade outcomes using a cluster-randomized three-arm trial design in 480 HCV-infected patients at 12 OAT clinics

randomized to standard of care (N=160) versus SHIM with (N=160) or without (N=160) ECHO facilitation.

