### 3.5.1 Design overview

Individual randomization of subjects within each site would likely lead to a high degree of cross-contamination between the study groups because the selected interventions are designed to sustainably change the provider knowledge and practice. Therefore, we have chosen a cluster-randomized trial design, where participating sites will be randomly assigned to one of the three implementation arms. Based on our preliminary studies suggesting region-specific differences in HCV level among OAT patients, we will stratify 12 OAT sites by 4 defined geographic regions (Center, East, South, West) at a 1:1:1:1 ratio. To achieve the desired sample size (see Sample Size section) and retain equal size in each group, we will select and match 3 clinics across the 4 regions. One clinic per triplet will be randomized to one of the three arms: Standard of Care, SHIM and SHIM+ECHO (see Study Conditions), resulting in total 4 clinics per arm. Each clinic will aim to recruit 40 patients. In case of clinic's capacity the availability of DAA medication in region, the clinic's capacity to include in treatment and monitor the course of treatment of a larger number of patients) the number of participants can be increased up to 60). All sites will follow the same patient recruitment and data collection procedures.

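### Section 3.4.5 states power above 0.95 for a synergistic ECHO effect that the three arms cannot separate from the added effect of ECHO given SHIM

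*Combined protocol and SAP*

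**What the plan says.** Section 3.4.5, the power text for Aim 2, states that "a sample size of 900 patients, provides more than sufficient power to conduct the proposed analyses" and that "as few as 200-300 participants in each group is more than sufficient to achieve sufficient power (>0.95". It then extends that power to further effects: "sufficient power (>0.95) to detect an intervention effect, including a synergistic effect of intervention". The synergistic term is written as a product of an intervention [No ECHO] term and an intervention [ECHO] term. The same sentence goes on to effects by site type and over time. It gives no effect size, event rates, intraclass correlation, significance level or formula.

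The randomisation is described in section 3.5.1: "One clinic per triplet will be randomized to one of the three arms: Standard of Care, SHIM and SHIM+ECHO", "resulting in total 4 clinics per arm", and "Each clinic will aim to recruit 40 patients". The opening of section 3.5 gives the arm sizes: "randomized to standard of care (N=160) versus SHIM with (N=160) or without (N=160) ECHO facilitation". SOC clinics refer patients elsewhere for screening and treatment (section 3.1.1). Their staff are asked about mentoring of the ECHO kind only as a hypothetical (section 3.4.2).

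**The concern.** Synergy has a definite meaning: the two components together do more than the sum of what each does alone. Assessing it needs outcomes under four conditions: neither component, SHIM alone, ECHO alone, and both. The trial observes three of them. The plan therefore states a power for an effect that its arms do not identify, and more patients would not change that.

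ECHO's contribution is one of the trial's two main hypotheses (Summary and section 3.5.8), so readers need to know exactly what the trial can say about it. The contrast it can estimate, SHIM+ECHO versus SHIM, answers whether ECHO adds anything to SHIM. It does not answer whether the two are more than additive. If 3.4.5 were taken as licence to report that contrast as synergy, a purely additive benefit would carry the wrong name.

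**Working it through.** **1. The plan's own figure.** Section 3.4.5 supplies no inputs, so its power cannot be reproduced as stated. The nearest check borrows the standardised effect of 0.20 from section 3.5.9, reads it as Cohen's w for a three-group comparison (2 df, two-sided 5%) and ignores clustering. The noncentrality is N × w².

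- N = 600 (3 × 200): 600 × 0.04 = 24, power 0.995.
- N = 900 (3 × 300): 900 × 0.04 = 36, power above 0.999.

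On these borrowed inputs, a figure above 0.95 is plausible for a general difference between arms at the sample sizes 3.4.5 cites. It says nothing about synergy.

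**2. Is the synergistic term estimable?** The notation allows two readings.

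*SHIM yes/no and ECHO yes/no.* The mean is b0 + b1·SHIM + b2·ECHO + b3·SHIM·ECHO, and the rows are:

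| Arm | Intercept | SHIM | ECHO | SHIM × ECHO |
|---|---|---|---|---|
| SOC | 1 | 0 | 0 | 0 |
| SHIM | 1 | 1 | 0 | 0 |
| SHIM+ECHO | 1 | 1 | 1 | 1 |

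The last two columns are identical, so the rank is 3 for 4 parameters. SHIM minus SOC estimates b1. SHIM+ECHO minus SHIM estimates b2 + b3, and only that sum. Isolating b3 requires

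b3 = (SHIM+ECHO − SHIM) − (ECHO only − SOC),

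and the ECHO-only mean is never observed.

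*Indicators for the SHIM-only and SHIM+ECHO arms.* No clinic is in both arms, so the product is 0 for every patient and the rank is again 3 of 4.

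Neither result depends on sample size, significance level, effect size or intraclass correlation. Setting b2 = 0 (ECHO does nothing without SHIM) makes b3 equal to SHIM+ECHO minus SHIM, but that is an assumption and the data cannot check it.

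**3. Power for the contrast that is estimable.** For SHIM+ECHO versus SHIM, take 160 per arm in 4 clinics of 40, two-sided 5%. The standardised differences d are assumptions: 0.20 and 0.32 are numbers borrowed from section 3.5.9, where they describe other comparisons, and 0.40 extends the range. The ICC is also assumed, since the plan gives none.

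- Design effect DE = 1 + (40 − 1) × ICC; effective n per arm = 160 / DE.
- Normal approximation: power = Φ(d / √(2/n_eff) − 1.96).
- Small-cluster version: noncentral t with 8 − 2 = 6 df and the same noncentrality. It ignores the regional triplets.

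| ICC | DE | n_eff | d = 0.20 | d = 0.32 | d = 0.40 |
|---|---|---|---|---|---|
| 0 | 1.00 | 160.0 | 0.43 / 0.33 | 0.82 / 0.67 | 0.95 / 0.84 |
| 0.01 | 1.39 | 115.1 | 0.33 / 0.25 | 0.68 / 0.53 | 0.86 / 0.72 |
| 0.02 | 1.78 | 89.9 | 0.27 / 0.21 | 0.57 / 0.44 | 0.77 / 0.61 |
| 0.05 | 2.95 | 54.2 | 0.18 / 0.14 | 0.39 / 0.29 | 0.55 / 0.42 |
| 0.10 | 4.90 | 32.7 | 0.13 / 0.11 | 0.25 / 0.19 | 0.37 / 0.28 |

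(Each cell: normal approximation / t with 6 df.) Example: d = 0.40 and ICC 0.05 give 0.40 / √(2/54.2) = 2.08, and Φ(2.08 − 1.96) = 0.55. So the figure in 3.4.5 cannot simply be moved to this contrast under a new name.

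**4. Sample sizes in the same paragraph.** The 900 patients and 200–300 per group do not match 480 and 160. Section 3.5.1 says "the number of participants can be increased up to 60" per clinic, which allows at most 4 × 60 = 240 per arm and 12 × 60 = 720 in total.

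**The case against.** The strongest reply is that nothing in the analysis depends on this clause. The Aim 2 analysis (section 3.4.4) uses principal components and a mixed model with barrier and facilitator components. The Aim 3 analysis (section 3.5.8) compares arms, tests ECHO against No ECHO and fits a trend across the three levels. It mentions moderation regression, but names no SHIM x ECHO term. The sample-size justification in section 3.5.9 makes no synergy claim. All of this stands, and it limits the practical impact.

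Three stronger readings are tempting, and the documents do not support them.

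- *The trial will report false synergy at far above the 5% level.* No synergy test is specified. If ECHO truly adds to SHIM, rejecting equality of SHIM+ECHO and SHIM is the correct answer to the second hypothesis, and only the label would be wrong. How often that could arise depends on assumed rates. With the 6-df method above, 30% versus 60% gives about 98%, 78% and 57% rejection at ICC 0.01, 0.05 and 0.10; 30% versus 40% gives about 27%, 15% and 11%. These are rates of possible mislabelling, not type I error.
- *The figure above 0.95 has nothing behind it.* It attaches first to a general intervention effect, for which it is plausible on the borrowed inputs. Effects by site type and over time are arm-by-covariate and arm-by-time terms, estimable in principle.
- *The design is wrong to omit an ECHO-only arm.* ECHO is presented as support for delivering SHIM (Summary and section 2), so its effect without SHIM may be of little interest. A reader may also find it reasonable to assume ECHO does nothing at SOC clinics. Under that assumption the interaction equals the added effect of ECHO, but the plan does not state it and the trial cannot test it.

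**Conclusion.** The point holds as an unsupported power statement in the Aim 2 text. With SOC, SHIM and SHIM+ECHO as the only arms, a SHIM x ECHO interaction is aliased with the added effect of ECHO given SHIM: rank 3 for 4 parameters, under either reading of the notation and at any sample size. The conclusion rests on the arm structure alone. The single exception is the assumption that ECHO without SHIM has no effect.

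The scope is narrow: one clause of one sentence, with no listed analysis built on it. The powers in the table rest on assumed effect sizes and ICCs and are not needed for the main conclusion. They show only that a replacement power for SHIM+ECHO versus SHIM needs its own inputs.

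**What to change.** In section 3.4.5, delete the synergy clause and the power attached to it. In its place, state that:

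- the design estimates two effects, SHIM versus SOC and SHIM+ECHO versus SHIM, the latter being the added effect of ECHO given SHIM;
- a SHIM x ECHO interaction is not estimable because no arm receives ECHO without SHIM, and it will be neither tested nor claimed.

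If a power for SHIM+ECHO versus SHIM is kept, compute it for 160 per arm in 4 clinics of 40, and give the effect size, significance level and assumed ICC, with a range for the ICC. Reconcile the 900 and 200–300 per group in the same edit.

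The cost is protocol and SAP wording plus one short calculation. No arm, site, patient or procedure changes, and nothing estimable is lost.

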### 3.5.1 Design overview

Individual randomization of subjects within each site would likely lead to a high degree of cross-contamination between the study groups because the selected interventions are designed to sustainably change the provider knowledge and practice. Therefore, we have chosen a cluster-randomized trial design, where participating sites will be randomly assigned to one of the three implementation arms. Based on our preliminary studies suggesting region-specific differences in HCV level among OAT patients, we will stratify 12 OAT sites by 4 defined geographic regions (Center, East, South, West) at a 1:1:1:1 ratio. To achieve the desired sample size (see Sample Size section) and retain equal size in each group, we will select and match 3 clinics across the 4 regions. One clinic per triplet will be randomized to one of the three arms: Standard of Care, SHIM and SHIM+ECHO (see Study Conditions), resulting in total 4 clinics per arm. Each clinic will aim to recruit 40 patients. In case of clinic's capacity the availability of DAA medication in region, the clinic's capacity to include in treatment and monitor the course of treatment of a larger number of patients) the number of participants can be increased up to 60). All sites will follow the same patient recruitment and data collection procedures.

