## 3 Study Design and Research Methods

### 3.1 Study conditions

#### 3.1.1 Standard of care (SOC)

As of today, HCV diagnostics and treatment is available through the network of specialized infectious diseases clinics. Other clinics (primary care, secondary level or clinics with other specialization) may prescribe and in some cases perform HCV screening, and in case of positive test result provide referrals to the specialized infectious diseases clinics or departments (hepatology centers). Upon admission, physicians are prescribing diagnostic tests to confirm the diagnosis, determine fibrosis stage, and detect possible contraindications. Based on the diagnosis and availability of medications, a treatment regimen is prescribed. Despite the fact that current MoH policy is permitting the use of international clinical guidelines, such as WHO or EASL, in routine practice the number and choice of diagnostic tests and treatment regimens is left to physician's discretion. In most cases, patients are required to have blood biochemistry (liver enzymes), quantitative HCV RNA, genotyping, liver ultrasound, FibroScan, kidney function tests. The cost of diagnostic tests is fully paid by the patients. The choice of treatment regimens usually includes the generic SOF formulations procured by the MoH or regional programs (see Rationale), or other DAA generics that recently became available for purchase at pharmacies. Hepatology center physicians are also prescribing follow-up tests (HCV RNA) to monitor treatment effectiveness.

In this study, the OAT clinics in the SOC arm will be informed of availability of medications at the hepatology centers and instructed to refer patients for screening (to primary care or other clinics, or harm reduction programs) and treatment (to hepatology centers).

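### Section 3.5.1 lets a clinic's sample grow from 40 to 60 on a treatment-capacity condition that is undefined for SOC clinics and need not be settled before allocation

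*Combined protocol and SAP*

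**What the plan says.** - **Clinic size (Section 3.5.1).** "Each clinic will aim to recruit 40 patients", but "the number of participants can be increased up to 60". Two conditions are given: "the availability of DAA medication in region", and sufficient capacity at the site, worded as "capacity to include in treatment and monitor the course of treatment of a larger number of patients) the number of participants can be increased". There is no threshold, decision-maker or date, and no requirement that the three clinics of a triplet move together.
- **Equal arms.** The same section matches clinics in regional triplets, partly to keep the groups the same size, "resulting in total 4 clinics per arm". The Aim 3 statement in Section 3.5 has clinics "randomized to standard of care (N=160) versus SHIM with (N=160) or without (N=160) ECHO facilitation".
- **SOC clinics do not treat HCV.** Section 3.1.1 has them "instructed to refer patients for screening (to primary care or other clinics, or harm reduction programs) and treatment (to hepatology centers"). Section 3.5.6 expects every SOC participant to receive HCV care away from the OAT clinic.
- **When recruitment stops.** Section 3.5.3 ends recruitment at the target, without saying where between 40 and 60 the target lies. Section 3.5.2 randomises once three sites per region are chosen and is silent on size.
- **Analysis (Section 3.5.8).** The cascade denominator is all enrolled participants. The primary model is a repeated-measures mixed model adjusted for region, age and gender. A second model is a logit mixed model grouped by arm or region. Neither names a clinic effect or clinic weights. A site random effect is named only for Aim 2, in Section 3.4.4.

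**The concern.** In a cluster trial with four clinics per arm, the number recruited at each clinic decides how much that clinic counts, unless the analysis says otherwise. Here that number may depend on whether a clinic can take on and monitor more HCV treatment. This is a natural question for a SHIM clinic and an undefined one for a clinic that refers treatment out. It is also plausibly related to P2 (starting DAA) and P3 (SVR12).

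So clinic weights may come to depend on the arm, through something close to the outcome. Part of the difference between arms could then reflect which clinics were enlarged and not how patients were cared for. The equal arm sizes that the triplet matching is meant to secure could also be lost.

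**Working it through.** **Inputs.** From the plan: 40 per clinic, maximum 60, four clinics per arm, 12 in all. The plan gives no clinic-level rates and no intracluster correlation (ICC), so those below are assumptions.

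**1. The plan's own figures.** 4 × 40 = 160 per arm and 12 × 40 = 480 in total; both reproduce. If every SHIM and SHIM+ECHO clinic grew and no SOC clinic did, the arms would be 160/240/240, or 640 in total. If all 12 grew, the total would be 12 × 60 = 720.

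**2. Weight of one enlarged clinic beside three of 40.**
- Pooled patients: 60/(60 + 3 × 40) = 33.3%, against 25% planned; the others carry 40/180 = 22.2% each.
- With a clinic random effect, the weight is approximately n/(1 + (n − 1) × ICC). At ICC 0.05 a clinic of 60 gets 60/3.95 = 15.19 and a clinic of 40 gets 40/2.95 = 13.56. The share is 15.19/(15.19 + 3 × 13.56) = 27.2%. It is 30.4% at ICC 0.01 and 26.2% at ICC 0.10.

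**3. Shift in a pooled arm percentage when two of four clinics grow to 60.**

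| Assumed clinic rates | All at 40 | Highest two at 60 | Lowest two at 60 | All four at 60 |
|---|---|---|---|---|
| 90/80/60/50% | 70.0% | (54+48+24+20)/200 = 73.0% | (36+32+36+30)/200 = 67.0% | 70.0% |
| 95/90/50/45% | 70.0% | (57+54+20+18)/200 = 74.5% | (38+36+30+27)/200 = 65.5% | 70.0% |

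The shift runs from −4.5 to +4.5 points in these examples and includes zero. Its sign depends on which clinics grow.

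**4. The same shifts with a clinic random effect, ICC 0.05.** With two enlarged clinics, each has a share of 15.19/(2 × 15.19 + 2 × 13.56) = 26.4%, which is 1.42 points above 25%. For 90/80/60/50% the shift is 0.0142 × (170 − 110) = 0.9 points. For 95/90/50/45% it is 0.0142 × (185 − 95) = 1.3 points.

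Other assumed spreads, with the best one or best two clinics growing:
- 50/60/70/80%: pooled +1.7 or +2.0 points; at ICC 0.05, +0.4 or +0.6.
- 30/50/70/90%: pooled +3.3 or +4.0 points; at ICC 0.05, +0.9 or +1.1.

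**5. Effect of the planned region adjustment alone.** With one clinic per arm in each region, a two-arm linear comparison adjusted for region weights each region by n₁n₀/(n₁ + n₀). That is 60 × 40/100 = 24 where only the SHIM clinic grows, and 40 × 40/80 = 20 elsewhere. Assume the same SOC rate in every region and growth in the two highest SHIM clinics. For 90/80/60/50%, the SHIM side becomes (24 × 170 + 20 × 110)/88 = 71.4%, a shift of +1.4 in place of +3.0. For 95/90/50/45%, it becomes (24 × 185 + 20 × 95)/88 = 72.0%, a shift of +2.0 in place of +4.5. Region adjustment reduces the shift but does not remove it.

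**6. No true effect, worst case.** With a mean of 50%, ICC 0.01 to 0.20, only SHIM clinics growing and growth perfectly tied to clinic rate, pooling favours SHIM by 0.6 to 3.0 points. With clinic random-effect weights the figure is 0.2 to 0.5 points.

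Steps 4 and 5 are approximations on the percentage scale; the planned logit model will not match them exactly.

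**The case against.** The strongest defence is that the rule is not aimed at any arm. DAA supply is a regional condition, shared by all three clinics of a triplet. Section 3.5.2 requires every site to have approval to receive DAAs. Section 3.5.1 does not limit growth to SHIM and says that all sites recruit in the same way. Extra participants come from the same randomly ordered Screening Log (Section 3.5.3), so no selection of individual patients is opened. The models are mixed models and adjust for region.

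Much of this stands, and it rules out several stronger readings that a reader might infer:

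- *That well-performing SHIM clinics will be enlarged.* The text says capacity; it does not tie growth to observed results.
- *That SOC clinics cannot grow.* They are not barred. They lack a defined meaning for one of the two conditions.
- *That the decision is taken after randomisation.* The timing is not stated.
- *That the bias must favour SHIM.* Step 3 shows it can go either way.
- *That the regional matching is undone.* Region adjustment offsets part of the imbalance.
- *That a 240-patient arm and a shift of 3 to 4.5 points occur together.* They cannot: 240 needs all four clinics at 60, and then the arm's percentage does not move.

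The defence does not close the gap. A shared recruitment procedure governs how patients are sampled, not how many each clinic takes. Calling a model mixed, with repeated measures, does not establish that clinic is one of its random effects.

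**Conclusion.** The point holds as a design weakness of modest and uncertain size. As written, cluster size can depend on arm and on a trait related to P2 and P3. This conflicts with the plan's own equal-size aim and with 160/160/160, and the Aim 3 analysis does not guarantee protection.

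Under crude pooling with the assumed clinic rates, the arm percentage could move by up to 4.5 points in either direction, or not at all. A clinic random effect at ICC 0.05 brings the favourable shifts of +1.7 to +4.0 points in the two spreads listed under step 4 down to about +0.4 to +1.1. All of these sizes rest on assumed rates and an assumed ICC, and on growth being related to clinic rate. The documents establish the opening, not that a bias will occur.

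**What to change.** Replace the expansion sentence in Section 3.5.1 with wording to this effect: *The number of participants per clinic (40, or one common number up to 60) is fixed for each regional triplet before that triplet is randomised. It is the same for all three clinics and is not changed after allocation.* This still permits 60 and removes the dependence on arm.

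If allocation has already happened, name a clinic random effect in the Aim 3 primary model in Section 3.5.8. Add a cluster-level sensitivity analysis that gives each clinic equal weight.

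The cost is one protocol sentence, or a short addition to the analysis plan. The downside is that a clinic with spare capacity cannot enrol beyond its triplet's common number.

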### 3.5.2 Site eligibility and selection

To participate in the study, each OAT site will need to meet the following criteria: (a) at least 100 patients receiving OAT; and (b) regional administrator approval for the site to receive the DAA medications and its clinicians to participate. Before the start of the first year of the main phase of the project there were 202 OAT sites in Ukraine, with 34 having over 100 patients (12, 10, 7, 5 sites in Center, East, South, West, respectively) and 21 have over 150 patients. OAT sites are minimally staffed with 1 narcologist and two nurses; the number of counselors and case managers may vary. After we define the three sites from each region, we will randomize them into one of the three study arms.

